**Table 4 Sample Size and Detectable Effect Size with 80% Power for Comparison of *Boostrix*-Exposed to Comparison**

Endpoint	N in Each Group	Rate in Comparison Group	Relative Risk	Power 
Preterm delivery	1425	10% 	1.4	80%
SGA	1425	10% 	1.4	80%
Chorioamnionitis	1469	3%	1.7	80%

 All tests are two-sided with alpha = 0.05, based on Fisher's exact test. Calculations conducted using R.

 (Ferré, 2016)

 (CDC, 2017; Nellhaus, 1968; Olsen, 2010)

## 7.6. Data management

As per the OTIS/MotherToBaby Pregnancy Registry protocol, data are collected using maternal interview, medical record, and the pregnancy diary. Maternal interview data are recorded on hard copies of forms, and these forms will be retained by OTIS/MotherToBaby. These forms are considered the primary data sources for the registry. The interviews are semi-structured and follow interview data collection forms to ensure that all study questions are addressed. Data from each interview form is entered into the study database at the end of the interview by the same person who conducted the interview. Medical records are requested from the hospital of delivery (maternal and neonatal information), obstetric provider (maternal information), and pediatrician (neonatal/infant). When records are received and catalogued, data is abstracted by trained personnel from each record using a standard abstraction form and entered into the study database. Medical records and medical record abstraction forms are hard copies or electronic copies and are retained on a secure server or in locked files. Data from maternal interview and medical record abstraction forms are entered into a customized OTIS/MotherToBaby Pregnancy Registry database located in the Research Center and developed specifically for the OTIS/MotherToBaby Pregnancy Research Studies.

The database itself has built in range limits for key variables that prevent certain data entry errors. In addition, all data entry is validated for a series of predefined critical variables and a random subset are validated for non-critical variables. The registry statistician also conducts reviews of the cumulative data in the database for distributions and values that are illogical.

Access to the database is controlled by password, with different access privileges assigned. An audit log is built into the database to archive all such entry edits.

Hard copies of participant files and participant signed consent forms are kept in locked cabinets in locked file rooms, or electronically secured files, under the supervision of the study investigators.

### **7.6.1. Data handling conventions**

All prenatal exposures to medications and vaccines are coded using the Slone Drug Dictionary (<http://sites.bu.edu/slone-drug-dictionary/>).

Twins and higher order multiples are excluded from analyses of preterm birth and SGA infants due to inherent risk of that outcome.

Loss-to-follow-up status is designated if a participant withdraws from the study, or if the study staff are unable to contact the study participant within 12 months of the estimated end of pregnancy in order to obtain outcome information. Pregnancies that are lost-to-follow-up will not be included in the analysis for the primary and secondary outcomes.

Coding of outcomes is performed by the study staff using the definitions provided in the protocol. Sources of information on exposure and outcome are the participant and medical records.

Missing values for the critical data for OTIS/MotherToBaby studies are typically very few and nearly always less than 10%. Complete case analysis is planned and there is generally no need to include imputation strategies; however, depending on the prevalence of missingness, sensitivity analyses will be conducted. These will be documented in the SAP.

### **7.6.2. Resourcing needs**

Not applicable.

## **7.7. Data analysis**

### **7.7.1. Essential analysis**

A stepwise approach will be used for the analysis. The initial analysis will be descriptive and unadjusted. Where numbers permit, multivariable analyses will be conducted for the analyses to adjust for possible confounders.

#### **Statistical methods:**

A detailed SAP will be prepared and finalized prior to the conduct of any study analysis. Maternal characteristics will be summarized within each cohort for the annual progress and final reports.

**Table 5 Summary of Exposure Window for Selected Primary and Secondary Outcomes**

Outcome	Exposure Window
Preterm Delivery	1 st day of the 27 th week of gestation to the 5 th day of the 37 th week of pregnancy
SGA	1 st day of the 27 th week of gestation to the end of the pregnancy
Chorioamnionitis	1 st day of the 27 th week of gestation to the end of the pregnancy

For the binary endpoints of **SGA and Chorioamnionitis**, the comparison will be on the proportion of events occurring after the 1st day of the 27th week of gestation or the date of *Boostrix* vaccination (whichever comes later) between the *Boostrix*-exposed cohort and the comparison cohort. A point estimate of the crude (i.e., unadjusted) relative risk (RR) of the *Boostrix*-exposed cohort versus the comparison cohort, as well as its 95% confidence interval (CI) will be computed.

Due to the observational nature of the study, the above crude estimate of RR will be further adjusted for potential confounders using a propensity score (PS) approach, if there are a sufficient number of events (to be detailed in Statistical Analysis Plan). A complete list of potential confounders will be provided in a separate table for each outcome prior to the final analysis, based on scientific knowledge including literature review. In addition, all of the following three criteria will be applied in accordance with the definition of confounders (Greenland, 1999; Xu, 2018), to identify confounders to be included in the PS model: 1) by assessing each considered variable in a logistic regression model containing exposure and the outcome to determine if inclusion of that single covariate changes the estimate of the odds ratio for exposure by 10% or more; 2) standardized mean differences (SMD) greater than 0.1; 3) association with the outcome with p-value <0.2 in the unexposed group. Care will be taken not to include those variables that are strongly associated with the exposure but only weakly associated with the outcome (Brookhart, 2006).

The confounders identified above may be used to build the PS for exposure (Rosenbaum, 2002). R package ‘twang’ or similar R package available at the time of analysis will be used for this purpose, following which SMD will be used to check the balance of the covariates between the cohorts.

The primary analyses will be performed to estimate the causal relative risk using the method of inverse probability weighting (IPW) based on the PS. In the IPW approach, we will use stabilized weights that are further trimmed to be between 0.1 and 10 if necessary (Austin, 2015). The 95% CIs will be obtained using the bootstrap estimated variance and asymptotic normality, with 200 bootstrap samples.

A secondary analysis will be conducted using outcome regression, i.e., a logistic regression model will be fitted with the binary outcome (Y), and exposure (A) and propensity score (L) as regressors. Standardization will be performed to obtain the

estimated causal risk ratio (Hernán, 2019), which has the interpretation as the marginal or population averaged risk ratio. The CIs are obtained by bootstraps.

For the endpoint of **preterm delivery**, only pregnancies ending in delivery after the 1st day of the 27th week of gestation or the date of *Boostrix* vaccination (whichever comes later), enrolled prior to 37 weeks' gestation, and whose pregnancies result in a live-born singleton will be included in the analysis. Further, in the *Boostrix*-exposed group, exposure to vaccine must take place between the 1st day of the 27th week of gestation and before 36 weeks' and 5 days (allowing at least one day after vaccination for preterm delivery). Because women can meet criteria for eligibility for the study at arbitrary times following the 1st day of the 27th week of gestation, they may not be followed from the beginning of the relevant gestational age window. Those who experience the event prior to enrollment will never enter the study, leading to left truncation of the time to event. This can produce selection bias. In addition, vaccine exposure can occur on or any time after the 1st day of the 27th week of gestation in pregnancy, so exposure status is time-dependent. To address these issues, survival analysis methods will be used. Fleming-Harrington estimate at 37.0 weeks' gestation will be used to estimate the preterm delivery rate and 95% CI in each of the cohorts (Fleming, 1984; Pan, 1998). The Cox proportional hazards marginal structural model (MSM) incorporating time-dependent vaccine exposure and relevant covariates will be used to estimate the causal hazard ratio (HR) and 95% CI (Hernán, 2001).

There may be potential biases in individuals who do or do not meet the requirement of releasing medical records in order to be eligible for inclusion in the study. Comparisons on key baseline covariates for those who were excluded from eligibility solely on the basis of medical records availability will be compared to those included in the study.

There may be potential biases involved in changing definitions of selected study outcomes over time. For example, criteria for preeclampsia/eclampsia have been modified in recent years. A sensitivity analysis (below) is planned to address this issue.

There can also be a "healthy vaccinator" bias which is a potential confounder that may be difficult to control for. In other words, women who elect to receive the *Boostrix* vaccine may have other lifestyle characteristics that are unmeasured or poorly measured that are associated with the pregnancy and infant outcomes of interest. A sensitivity analysis (below) to address this issue.

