Gestational age at study enrollment	Confounder	Maternal report	Weeks of pregnancy at time of enrollment, continuous and categorical ( $\leq 13$ , 13.1-19.9, $\geq 20$ ): gestational age is calculated from the first date of LMP
Referral source	Confounder	Maternal report	Source options: Sponsor, OTIS service, health care provider, Internet, Other.
Prenatal, Multivitamin, or Folic acid	Confounder	Maternal report	Prenatal, Multivitamin or Folic Acid supplement use by timing (began prior to conception, post-conception only, not taken at all)
Alcohol use in pregnancy	Confounder	Maternal report	Yes/No. Dose and frequency are captured

Variable	Role	Data Source(s)	Operational Definition
Tobacco use in pregnancy	Confounder	Maternal report	Yes/No. Dose and frequency are captured
Medication and vaccine use in pregnancy	Confounder	Maternal report	Prescription and over-the-counter medications, vaccines are captured for the period from the first day of LMP through the end of pregnancy; dose, frequency, duration, and indication including stop and start dates are collected
Maternal pregnancy exposure to a known human teratogen	Confounder	Maternal report	Maternal pregnancy exposure to a known human teratogen
Comorbid maternal medical history	Confounder	Maternal report Medical record	Comorbid maternal medical history (e.g., chronic hypertension, asthma)
Current pregnancy ending in a major birth defect	Confounder	Maternal report Medical record	A major structural or chromosomal defect that has either cosmetic or functional significance to the child (e.g., a cleft lip) classified using CDC coding criteria

Methods for identifying and controlling for these confounders and/or effect modifiers are described in Section 7.7.1. The SAP will provide greater detail on the definitions of, the identification of and the controlling for confounders and/or effect modifiers.

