### 7.7.2. Sensitivity analyses

To address changes over time in diagnostic criteria for preeclampsia/eclampsia, year of enrollment will be considered as a potential confounder in analyses. However, an additional sensitivity analysis will be conducted by stratifying the analysis on data collection prior to and after the year the diagnostic criteria modifications were implemented.

In addition, if major discrepancies are identified by descriptive analysis of baseline characteristics and outcomes for the participants previously enrolled in the OTIS/MotherToBaby Pregnancy Registry and the participants newly enrolled over 4

years, further exploratory stratified analyses could be conducted, provided the sample size allows for it.

To address potential unmeasured confounding associated with being a “healthy vaccinator”, a second sensitivity analysis will be conducted restricting the sample in each cohort to those who received the recommended influenza vaccination in pregnancy. This ensures that both the exposed and comparator groups were at least compliant with one vaccine recommendation in pregnancy.

Although major birth defects are not expected to be causally related to Tdap vaccination exposure that takes place long after completion of embryogenesis when most major birth defects occur, major birth defects will be considered as a potential confounder in analyses. For example, prenatal diagnosis of a major birth defect could influence willingness to receive a Tdap vaccination later in pregnancy. In turn the major birth defect could independently influence risk of stillbirth, PTB or SGA. To further address this issues, a third sensitivity analysis will be conducted excluding infants in both cohorts with documented major birth defects.

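### The rule that a covariate must pass all three screens to enter the propensity score drops most moderate confounders, and can leave material bias in the adjusted relative risks for SGA and chorioamnionitis

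*Protocol*

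**What the plan says.** Section 7.7.1, under the SGA and chorioamnionitis analyses, starts from subject matter: "A complete list of potential confounders will be provided in a separate table for each outcome prior to the final analysis". It then sets a data-driven rule. The protocol states that "all of the following three criteria will be applied in accordance with the definition of confounders", and gives the purpose as "to identify confounders to be included in the PS model". The three criteria are:

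1. adding the covariate on its own "changes the estimate of the odds ratio for exposure by 10% or more";
2. the cohorts differ on the covariate by an SMD above 0.1;
3. the covariate is related to the outcome at p below 0.2 among unexposed women.

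The covariates identified in this way may then be used to build the propensity score (PS). The primary analysis (stabilized inverse probability weighting) and the secondary analysis (outcome regression with the PS as regressor, then standardization) both rest on that score. No covariate is stated to enter regardless of the screens. Section 7.7.2 says only that year of enrollment and major birth defects will be considered as potential confounders.

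**The concern.** The 10% criterion judges covariates one at a time, but confounding accumulates across them. A variable that is plainly a confounder on subject-matter grounds can shift the estimate by 3 to 7%, fail the screen and be discarded. Four or five of these acting in the same direction can shift the estimate by 20% or more. Table 2 lists many candidates that could be of this moderate kind, such as age, education, socioeconomic category, BMI, smoking and reproductive history.

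Both adjusted analyses use the same PS, so the secondary one cannot reveal what the primary one left out. SGA is a primary outcome, and the adjusted RR is the study's causal estimate for it. Residual bias away from the null could create a false safety signal; bias toward or below the null could conceal a real one.

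**Working it through.** The protocol gives no figure for the performance of the selection rule, so there is none to reproduce.

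**Inputs from the protocol.** SGA: 1,425 per cohort and a 10% rate in the comparison group. Chorioamnionitis: 1,469 per cohort and 3% (both Table 4). Three screens, all required; stabilized weights trimmed to 0.1 to 10 (section 7.7.1).

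**Assumptions, not in the protocol.** Number, prevalence, strength and direction of the confounders; true RR = 1 unless stated. In the simulations a logistic PS stands in for the twang fit.

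**One covariate, by hand.** Take prevalence 15% in the exposed and 10% in the unexposed.

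- SMD = (0.15 − 0.10)/√[(0.15×0.85 + 0.10×0.90)/2] = 0.05/0.330 = 0.15, above the 0.1 cut-off.
- Bias factor on the RR scale for outcome risk ratio r: (1 + 0.15(r−1))/(1 + 0.10(r−1)). For r = 2: 1.15/1.10 = 1.045. For r = 3: 1.30/1.20 = 1.083. For r = 3.5: 1.375/1.25 = 1.10.
- The screen uses the odds ratio, which moves slightly more. For r = 2 and 10% risk in the unexposed, the risk in the exposed is 0.10×1.045 = 0.1045. The crude OR is (0.1045/0.8955)/(0.10/0.90) = 1.05. For r = 3 the OR shift is about 9.3%, and 10% is reached at r of about 3.2.

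So at this imbalance, a covariate that doubles the risk moves the OR by about half of what the screen demands.

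**Four such covariates together.** 1.045⁴ = 1.19. Each fails the screen alone; jointly they bias the RR by 19%.

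**Simulation of the full rule in this setting** (SGA size and rate). The rule kept 0.007 to 0.01 of 4 covariates on average. The screened RR was 1.19 to 1.20, and the nominal 5% test rejected in 38 to 45% of datasets. With all four in the PS, the RR was 1.00 to 1.01 with rejection in 4.5 to 6%.

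**Probability that one true confounder passes all three screens** (4,000 datasets per setting, prevalence 10% or 30% in the unexposed):

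| Confounder | SGA | Chorioamnionitis |
|---|---|---|
| SMD 0.15–0.2, OR 1.5–2 | 0–4% | 0–10% |
| SMD 0.3, OR 1.5 | 1–2% | 6–9% |
| SMD 0.3, OR 2 | 23–47% | 31–45% |
| SMD 0.2, OR 3 | 34–57% | 44–57% |
| SMD 0.3, OR 3–4 | 95–100% | 85–100% |

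The 10% screen is usually the binding one. For chorioamnionitis the p<0.2 screen also removes many weaker covariates (passed in 42 to 53% of datasets at OR 1.5).

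**Residual bias with other mixes** (400 datasets each). A false signal here means a lower 95% limit above 1.

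| Confounders | Outcome | Kept | Screened RR (false signal) | All in PS: RR (false signal) |
|---|---|---|---|---|
| 5 with SMD 0.2, OR 1.5 | SGA | 0.00 of 5 | 1.20 (38.5%) | 1.00 (1.0%) |
| 5 with SMD 0.2, OR 2 | SGA | 0.06 of 5 | 1.34 (77%) | 1.01 (3.7%) |
| 5 with SMD 0.2, OR 1.5 | Chorioamnionitis | 0.02 of 5 | 1.24 (19%) | 1.02 (3.0%) |
| 5 with SMD 0.2, OR 2 | Chorioamnionitis | 0.32 of 5 | 1.35 (36%) | 1.01 (1.5%) |
| 1 strong + 4 moderate | SGA | 1.00 of 5 | 1.14 (23.5%) | 1.00 (2.0%) |
| 3 strong (SMD 0.3, OR 4) | SGA | 2.92 of 3 | 1.01 (3.7%) | 1.00 (1.8%) |

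**Reverse direction.** If the four covariates are instead commoner in the unvaccinated, the factor is 1/1.19 = 0.84 (0.84 to 0.85 allowing for rounding and simulation error). A true RR of 1.4, the SGA effect size in Table 4, would then appear as about 1.4 × 0.84 = 1.17. By the normal approximation at 1,425 per cohort and 10%, power is about 91% for RR 1.4 and about 31% for RR 1.17. Table 4 gives 80% at RR 1.4; 80% is in fact reached at about 1.345, so 1.4 looks rounded up, and this does not affect the point.

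**The case against.** The best case for the rule has four parts.

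- **Strong confounders survive.** This stands. It would be wrong to infer that the rule drops real confounders almost every time: at SMD 0.3 and OR 3 to 4 they pass in 85 to 100% of datasets, and with three such confounders the screened SGA estimate is about 1.01.
- **The bias depends on unstated inputs.** This also stands. If one of the four covariates acts in reverse, the bias falls to 1.045² = 1.09; if two do, it cancels. It cannot be said that the adjusted estimates will stay confounded, only that the rule gives no protection if moderate confounders align.
- **The wording might be additive.** The screens are introduced as an addition to the list. But the insistence on all three, their stated purpose and the reference back to the confounders so identified favour a filter.
- **Detail is left to the SAP.** The rule and its thresholds are fixed in the protocol, so further detail would not remove them.

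A reader might infer more, and the protocol does not support it:

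- **Post-vaccination covariates.** Table 2 says that "vaccines are captured for the period from the first day of LMP through the end of pregnancy", but that is a data-capture window, start and stop dates are recorded, and covariate definitions are left to the SAP.
- **Influenza restriction.** The sensitivity analysis "restricting the sample in each cohort to those who received the recommended influenza vaccination in pregnancy" is a separate matter, and nothing here bears on it.
- **Stillbirth.** Adjustment is conditional on a sufficient number of events, so it may never be run.
- **Confidence intervals.** The protocol does not say whether each bootstrap sample repeats the selection, so intervals that are too narrow would be conjecture.
- **Preterm hazard ratio.** That model refers only to relevant covariates; the three screens are not stated there.

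**Conclusion.** The point holds for SGA and chorioamnionitis. As written, the rule can exclude any literature-listed confounder, and it excludes moderate ones in roughly 90 to 100% of datasets. Under the stated assumptions, four or five aligned moderate confounders leave an RR of about 1.19 to 1.34 for SGA, and five leave 1.24 to 1.35 for chorioamnionitis, when the truth is 1. The upper SGA figure is close to the 1.4 that the study is sized to detect. With a healthy-vaccinator pattern, which section 7.7.1 itself anticipates, the same mechanism would plausibly run the other way and could mask a real risk. The size depends on the number, strength and direction of such confounders, which the protocol does not give. It is small when confounding is dominated by a few strong variables, or when the moderate ones oppose each other.

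**What to change.** Change the wording of section 7.7.1, and carry it into the SAP before any outcome analysis:

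- The prespecified subject-matter confounders for each outcome enter the PS regardless of the three screens.
- The screens may only add covariates to that list, or define a sensitivity analysis reported alongside.
- SMD is used to check balance after weighting, over the whole list, and not as a condition of entry.

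The existing caution against variables strongly tied to exposure but only weakly to outcome can be applied when the list is drawn up. Few outcome events are no obstacle to holding the full list, because the PS models exposure, with a target of 1,500 per cohort. The cost is a small loss of precision from covariates weakly related to the outcome. No new data are needed.

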9. comparison of proportion of NICU admissions for bronchopulmonary dysplasia occurring in pregnancies ending in live birth including twins or higher order multiples between the *Boostrix*-exposed cohort and the comparison cohort by calculating relative risks and associated 95% confidence intervals.

Initial analysis will be unadjusted. Adjusted analyses will be conducted where numbers of events permit, multivariable analyses will be conducted to adjust for possible confounders.

For the *Boostrix*-exposed cohort, follow-up time with respect to the primary and secondary outcomes will start on the date of *Boostrix* vaccination, and for the comparator cohort, follow-up time will start on the 1st day of the 27th week of gestation.

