## 5. RATIONALE AND BACKGROUND

### 5.1. Background

A US *Boostrix* pharmacovigilance pregnancy registry was initiated in 2005 ([Kuznetsova, 2022](#)) when *Boostrix* was licensed in the United States (US) for active booster immunization against diphtheria, tetanus, and pertussis (Tdap) in individuals aged 10 years and older. In June 2011, the US Advisory Committee on Immunization Practices (ACIP) recommended immunization of pregnant women against pertussis as a mean to protect their infants, who are vulnerable until they can receive their primary vaccination. ([CDC, 2013](#)). In October 2012, ACIP recommended that the Tdap vaccine be given to women during every pregnancy (preferably between 27–36 weeks gestation). Since 2014 the maternal Tdap uptake measured by surveys conducted by the US Centers for Disease Control (CDC) has plateaued at 55% ([Baïssas, 2021](#)). Two Tdap vaccine brands are used for immunization during pregnancy in the US ([CDC, 2017](#)).

The previous *Boostrix* US pregnancy registry EPI-PERTUSSIS-028 VS US PR (201327) was aimed at assessing the proportion with any abnormal pregnancy outcomes among registered pregnancies (women vaccinated with *Boostrix* during pregnancy or within 28 days preceding conception). From May 2005 to August 2019, 1,517 (1,455 prospective

and 62 retrospective) pregnancy reports were received from the pregnancy registry (Kuznetsova, 2022). Of the prospective reports, there were 1,188 lost to follow-up and 250 had known outcomes: 244 live infants with no apparent birth defects, 3 live infants with birth defects, and 3 spontaneous abortions with no apparent birth defects. Data from the *Boostrix* US pregnancy registry EPI-PERTUSSIS-028 VS US PR (201327) raised no safety concerns regarding *Boostrix* maternal immunization (Kuznetsova, 2022). However, the findings from the registry were limited by the modest number of follow-up reports (N=250) and the lack of representativeness of all pregnancies, the high proportion of loss to follow-up and the absence of a comparison cohort who were unexposed to Tdap vaccination during pregnancy.

On October 7 2022, the US Food and Drug Administration approved *Boostrix* for immunization during the third trimester of pregnancy to prevent pertussis in infants younger than two months of age (US FDA, 2022). This revised registry aims at monitoring the safety of *Boostrix* in this indication and is a postmarketing commitment.

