### **Cohort 2: Tdap Vaccine-Unexposed Comparator Group**

#### Inclusion Criteria

- Currently pregnant women at the time of enrollment who were not exposed to any Tdap vaccine from the first day of LMP to the end of pregnancy.
- Currently pregnant women at the time of enrollment who agree to the conditions and requirements of the study including informed consent, the interview schedule and release of medical records.
- Availability of obstetric, delivery and pediatric medical records for the enrollment pregnancy.

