#### Exclusion Criteria

- Women who have received a Tdap vaccine anytime during pregnancy.
- Women who have previously been included in this study with a prior pregnancy.

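### The Fleming-Harrington preterm rate is computed in a comparator cohort defined by never being vaccinated before delivery, which biases that rate upward; the start of exposed follow-up must also be reconciled with the time-dependent Cox model

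*Protocol*

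**What the plan says.** Section 7.7.1 observes that vaccination can occur at any time from the 1st day of the 27th week, "so exposure status is time-dependent", and calls for survival methods to deal with this and with left truncation. It then fixes two estimators:

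- **Rates:** "Fleming-Harrington estimate at 37.0 weeks' gestation will be used to estimate the preterm delivery rate and 95% CI in each of the cohorts".
- **Effect:** a Cox marginal structural model with time-dependent vaccine exposure, giving a hazard ratio.

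The cohorts are fixed by final status. In section 7.2.1, Cohort 2 consists of women "who were not exposed to any Tdap vaccine from the first day of LMP to the end of pregnancy", and its exclusion list repeats the rule: "Women who have received a Tdap vaccine anytime during pregnancy".

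Section 2 (Data Analysis) sets the follow-up start. Exposed women are counted only from their dose: "follow-up time with respect to the primary and secondary outcomes will start on the date of" that dose. Comparator women are counted from 26.0 weeks, the opening day of week 27. Section 5.1 puts maternal Tdap uptake at 55% from US surveys and adds: "Two Tdap vaccine brands are used for immunization during pregnancy in the US".

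**The concern.** Membership of the comparator cohort depends on the future. Take two women, both unvaccinated and pregnant at 30 weeks. The first delivers that week and becomes a Cohort 2 event. The second stays pregnant, is vaccinated at 33 weeks and leaves Cohort 2. Her weeks up to 33 are event-free unvaccinated time, but they are not in the comparator curve because she is not in that cohort. They are not in the exposed curve either, because that starts at vaccination. The comparator keeps the early events and loses part of the denominator.

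Delayed entry corrects for women who enrol late. It cannot correct a risk set from which women have been removed because of something that happens later.

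The affected figures are the reported absolute preterm rates, with 95% CIs, for a primary safety outcome. A reader who sets the two rates side by side would see a lower rate after vaccination even with no vaccine effect.

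**Working it through.** The protocol gives no figure for these rates, so there is nothing to reproduce. The check is what the stated rule yields when the vaccine has no effect.

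**Inputs from the protocol.** Uptake *u* = 0.55 (section 5.1). Preferred dosing window 27-36 weeks (sections 2 and 5.1). Comparator follow-up from 26.0 weeks, the 1st day of the 27th week. One true preterm risk is set at *p* = 10%, the comparator rate in Table 4.

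**Assumptions.** Vaccination is independent of risk. Doses are uniform over a window. Preterm births are uniform within these week bands:
- Timing A (*p* = 10%): 26-28 3%, 28-32 10%, 32-34 12%, 34-37 75%.
- Timing B (*p* = 8%): 26-28 5%, 28-32 14%, 32-34 13%, 34-35 12%, 35-36 20%, 36-37 36%.

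**Comparator formula.** Let *G(t)* be the share of eventual doses given by week *t*. A woman delivering at *t* is still undosed with probability 1 − *uG(t)*. Let *A* be the average of this over preterm delivery times. All doses are given before 37 weeks, so a woman reaching 37 weeks is undosed with probability 1 − *u*. In a cohort fixed by final status and followed from 26.0 weeks, the Fleming-Harrington estimate at 37.0 converges to the cohort's own event proportion:

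rate = *pA* / [*pA* + (1 − *p*)(1 − *u*)]

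It equals *p* only if *A* = 1 − *u*, that is, if every dose came before every preterm birth.

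**Worked case: timing A, doses over 27-36 weeks.** Mean *G* in the four bands is 0.028, 0.333, 0.667 and 0.926. The undosed probabilities are therefore 0.985, 0.817, 0.633 and 0.491.

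*A* = 0.03×0.985 + 0.10×0.817 + 0.12×0.633 + 0.75×0.491 = 0.555

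Rate = 0.0555 / (0.0555 + 0.90×0.45) = 0.0555 / 0.4605 = 12.1%, against a truth of 10.0%.

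**Exposed curve.** It enters at vaccination, so it starts at 27.0 weeks and estimates the risk among women undelivered then. Timing A: 1 − 0.90/(1 − 0.10×0.015) = 9.9%. Timing B: 1 − 0.92/(1 − 0.08×0.025) = 7.8%.

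**Results at 55% uptake, no vaccine effect:**

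| True risk, timing | Doses over weeks | *A* | Comparator | Exposed | Ratio |
|---|---|---|---|---|---|
| 10%, A | 27-36 | 0.555 | 12.1% | 9.9% | 0.82 |
| 10%, A | 27-32 | 0.488 | 10.7% | 9.9% | 0.92 |
| 8%, B | 27-36 | 0.569 | 9.9% | 7.8% | 0.79 |
| 8%, B | 27-32 | 0.507 | 8.9% | 7.8% | 0.88 |
| 8%, B | 27-30 | 0.488 | 8.6% | 7.8% | 0.91 |

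Early-peaked dose distributions under timing B, tried by simulation, gave 0.91-0.93. The upper end is soft. If every dose fell between 27.0 and 28.0 weeks, *A* under timing B would be 0.05×0.8625 + 0.95×0.45 = 0.471, the comparator rate 8.3% and the ratio 0.94.

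**Delayed entry.** A simulation of about 1.5 million pregnancies (10%, timing A) had 40% of women enrolling between 26 and 34 weeks and applied delayed entry. It gave the same comparator rates, 10.7% (27-32 weeks) and 12.1% (27-36), with 9.8% in the exposed. Delayed entry leaves the bias in place.

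**Other uptakes, same simulation:**

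| Uptake | Comparator rate (doses 27-32 to 27-36) | Ratio |
|---|---|---|
| 40% | 10.4-11.2% | 0.94-0.88 |
| 70% | 11.3-13.8% | 0.87-0.71 |
| 85% | 13.3-18.8% | 0.74-0.52 |

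**After the fix.** Taking the unexposed curve from all pre-dose person-time, with women censored at the dose, gave 9.9-10.0% in every scenario and ratios of 0.98-0.99. The small remainder arises because the exposed curve starts at 27.0 weeks rather than 26.0.

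**Cox model.** Section 7.7.1 makes exposure time-dependent, which implies that a Boostrix woman is unexposed until her dose. Section 2 starts her follow-up at the dose, so she would have no unexposed time. On that reading the unexposed risk set is again the never-vaccinated cohort and the hazard ratio carries the same kind of bias. The two statements cannot both govern the analysis.

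**The case against.** The strongest reply is that the Fleming-Harrington figures are not the comparison. Section 2 compares preterm birth by hazard ratios, and section 7.7.1 specifies a Cox model with time-dependent exposure. No ratio or test of the two rates is planned. This stands. A reader might infer that the primary comparison will make the vaccine look protective or hide a real increase. The documents do not support that: it would follow only if section 2's start of follow-up governed the Cox model, and the protocol leaves that unresolved.

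A reader might also infer that the hazard ratio is biased in any case, because women given the other Tdap brand are in neither cohort and because the cohorts are filled 1,500 to 1,500 by final status. These effects rest on figures the documents do not give. With half of vaccinees assumed to receive the other brand, the null hazard ratio was 0.95-0.97 at 55% uptake. Under 1:1 sampling it ran from 0.78 to 1.04 as uptake fell from 80% to 40%, so its direction is not fixed. The corrected unexposed rate under plain 1:1 sampling was 10.1-10.3% at 55% uptake against a truth of 10.0%, though 9.6-15.0% over uptakes of 40-85%. This supports a sensitivity analysis and no more.

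Finally, most analytic detail may be left to the SAP. But the protocol itself fixes the estimator, the cohort definitions and the start of follow-up, and the fault lies in how these combine.

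**Conclusion.** The point holds for the cohort-specific preterm rates. As written, the comparator rate is biased upward, and late-enrolment methods do not remove the bias. At 55% uptake with no vaccine effect the exposed/comparator ratio is about 0.79-0.93. It is nearest 1 when doses are given soon after 27 weeks, and it falls further as uptake rises. The direction follows from the cohort definition whenever some preterm births precede doses that would otherwise have been given. The size rests on assumed registry uptake, dose timing and preterm timing, and on vaccination being independent of risk.

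For the hazard ratio, the finding is a contradiction between section 2 and section 7.7.1 that decides whether the main bias is avoided; it is not a demonstrated bias. Severity: should be fixed before analysis.

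**What to change.** 1. In section 7.7.1, have the Fleming-Harrington rates estimated by time-dependent exposure status instead of by cohort.
2. Estimate the unexposed curve from all observed person-time before any Tdap dose, with entry at the later of enrollment and the 1st day of the 27th week and censoring at the dose. Estimate the exposed curve with entry at the later of enrollment and vaccination.
3. State that in the Cox model Boostrix women contribute unexposed time until their dose and exposed time afterwards, and reconcile the follow-up sentence in section 2 with this.
4. Add a sensitivity analysis of how the result depends on the mix of never- and not-yet-vaccinated women, for example by reweighting to registry proportions or adding other-brand women's pre-dose time where records exist. Formal inverse-selection weights are not well defined here, because section 7.2.1 takes previously enrolled women from the most recent year backwards until the sample is met.

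The cost of items 1-3 is wording and some programming. Item 4 needs extra record handling if other-brand women are added.
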